11. STUDY STRENGTHS/LIMITATIONS

Aim 1 Limitations:

Family planning register use: There are limitations in using program data from FP registers. These registers can have missing information or illegible entries. Also, some FP clinics may be using prior versions of FP registers that lack key information about cervical cancer screening. However, use of routinely collected register data is a main objective of IS and has

the advantage of scalability as new data sources are not required. This aims to keep programmatic costs low, and increase feasibility and scalability. To address issues with FP registers, any clinic-based logs will supplement data in FP registers.

Poor correlation between FP register data and DHIS reports: After discussions with members of the Mombasa County DOH, cervical cancer screening should be documented in both FP registers and DHIS reports. Results of this comparison will be presented to our County collaborators to find a solution for appropriate documentation. The County may decide to provide further guidance in register documentation to all FP clinics, or the County may decide that it is acceptable to use DHIS reports only for cervical cancer screening documentation. The current state of documentation for screening will guide the outcome assessment in Aim 2 (see C.2.B).

Screening outside FP clinics: The register abstraction process may not capture whether women have been recently screened. These women would appear to need screening and would be counted as a loss in the cascade. According to the DOH, the most common clinics for cervical screening are FP clinics and HIV clinics, but it is unclear where HIV-positive and HIV-negative women are actually accessing screening. The 2014 estimates (the most recent survey) of screening on the coast of Kenya suggest only 8% of women have ever been screened, which is higher than the 3-month screening prevalence of 0.6% in our preliminary data (C.1.E). Given this estimate, the possibility that a woman had been screened recently is expected to be quite low. Consequently, the vast majority of women require screening. Aim 1 will be used to explore how many clinics are performing any screening, the proportion of women screened, and if screening differs by HIV status. We are focusing on FP clinics, as women attending these clinics are generally expected to be sexually active, at risk for HPV infection, and consequently, cervical cancer. Some HIV-positive women could access screening in HIV clinics. We anticipate quantifying the care cascade separately by client HIV status to better illustrate the landscape of screening practices. Future work could also examine cervical cancer screening in HIV clinics.

Aim 2 Limitations:

New versus all FP clients: If prevalence of screening is found to be very low in Aim 1 (as we expect), the RCT will aim to improve screening for both new and existing FP clients. However, if Aim 1 screening prevalence is higher than expected (we anticipate a cut-off of around 20% screening prevalence), then including existing clients may lead to significant misclassification. In this scenario, Aim 2 will focus on new FP clients only. We anticipate having sufficient power for this alternative approach. Preliminary data suggest an average of 60 new FP clients per clinic in a 3-month period (C.1.E), which we would anticipate would continue throughout a 12-month period. Ten clinics per arm in the RCT with only 60 new clients per clinic would provide at least 80% power to detect a 12% difference between intervention and control arms.

Identifying women who should be screened: While it is a goal of IS studies to work within existing systems, the use of routinely collected FP register data to assess the RCT outcome has its challenges. It may be difficult to assess if a woman had been recently screened. This potential limitation may vary in women based on their HIV-status. Because screening for HIV-positive women is recommended annually, HIV-positive women who should be screened may be identified by collecting FP register data over a 12-month period. On the other hand, HIV-positive women may be accessing screening at HIV clinics and not FP clinics. In contrast to HIV-positive women, HIV-negative women should be screened every 5 years. As a result, data abstraction over a 12-month period may incorrectly identify women needing screening when they had recently been screened. The intervention then may appear to be more effective in HIV-positive women only because of the data abstraction period or alternatively, miss screening in HIV-positive women if it is occurring outside of FP clinics. We will use Aim 1 to understand screening practices for HIV-positive and HIV-negative women. We believe it will be reasonable to assume that the majority of women have not been screened recently, should be screened, and then counted in the outcome assessment. If our data in Aim 1 does not

support this assumption, we will adjust our approach depending on what we discover. For example, we may focus on HIV-negative women in the primary analyses as they would be less likely than HIV-positive women to have accessed screening elsewhere, or only include new FP clients as outlined in the first limitation. Alternately, we may find in Aim 1 that HIV-positive women are screened at HIV clinics and not FP clinics. To address differences in screening practices by HIV status, we may stratify results based on HIV status, or exclude HIV-positive women from our primary analysis. The cluster RCT design provides robust power with the same clinic numbers and varying clients in each clinic. Using our conservative estimates of clients per clinic, we will have a sufficient sample size to stratify by HIV status or exclude HIV-positive women from the analysis.

Current screening practices vary between FP clinics: It is possible that randomization would select a disproportionate number of clinics in either intervention or control arms that already perform screening. This may bias results. Aim 1 results will be used to decide whether to stratify randomization based on past screening rates.

SAIA interventions not readily identifiable or feasible: Clinic staff may not identify solutions to address bottlenecks. In discussions with [name] (based on his experience with both CQI and the development of SAIA), this can be addressed by highly trained, experienced study staff to guide clinic staff through SAIA. Additionally, other quality improvement tools like root cause analysis and fishbone diagrams can be helpful (57). It is also possible that solutions proposed by staff members may not be feasible. Study staff will help staff to identify solutions that are more feasible in the given context and budget.

Focus on cervical cancer screening: This study will focus on increasing screening and will not address the linkage to treatment for positive screens. While we recognize that referral and treatment are also important, these steps would add complexity to this small study, and we likely would not have sufficient power. In addition, we felt that focusing on screening provided a useful metric for evaluating whether SAIA is potentially effective for addressing cervical cancer prevention. To insure adequate care during the study, we will partner with our Mombasa County collaborators to work programmatically to ensure that women with positive screens are linked to treatment. The extension of SAIA to improve linkage to treatment is a potential aim of a future study.

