C.1.D. Adaptations of SAIA methods in ongoing trial, led by [name]. Adaptations of SAIA methods are currently being used to address linkage of HIV services in the ongoing trial “RCT of an implementation science tool to integrate HIV testing into family planning services” (K24 HD088229-01; PI, [name]; FP HIV SAIA Trial) with [name] (primary mentor) and [name] (co-mentor). To meet the national guideline that all women should be tested for HIV when accessing FP services (48), a data entry template for recording of HIV counseling and testing was integrated into the Kenyan FP registers in 2008. Our UW group is addressing this guideline in the FP HIV SAIA trial that compares SAIA to usual procedures to improve HIV testing at FP clinics in Mombasa County. A preliminary performance review of 60 FP clinics in Mombasa County collected data from FP registers and clinic manager interviews. Of 60 clinics, a total of 4389 new FP clients were seen in a 3-month period (mean of 73 new clients per clinic (standard deviation [SD] 81)). Only 23 clinics reported any HIV testing, with a total of 420 new FP clients screened in a 3-month period. Three of these clinics performed the majority of screening (302 screens, 72%). As a Senior Fellow in Infectious Diseases, [name] has led the implementation for this project. She prepared the applications for ethical and humans subjects approval in the US and Kenya, developed data collection tools, trained study staff, created the database, launched the study, and coordinated planning, logistics, and dissemination of findings with Mombasa County. This study has provided [name] with valuable experience in implementing SAIA, and demonstrates the great potential for additional implementation research in Mombasa.

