Aim 2: The FP HIV SAIA Trial preliminary results suggest that very little cervical cancer screening is performed or being documented in FP registers. Of these available data, the proportion of FP clients screened was 0.6%. Because this screening prevalence may not be representative, we have used a more liberal estimation of 8% prevalence of screening based on the 2014 DHIS estimates (the most recent resource available). FP clinics had an average of 183 clients in a 3-month period. Most clients follow-up every 3 months so this is a conservative estimate of total clients in a 12-month period. We will assume that following the intervention, 20% of women will be screened for cervical cancer. To calculate a sample size for a cluster RCT, the cluster size variability (κ) must be estimated with literature often citing $\kappa \leq 0.25$ and rarely exceeding 0.5 (54). We have estimated a κ of 0.5 to be conservative, which translates to an intra-class correlation coefficient of approximately 0.05. Cluster size variability of FP clinics was calculated as 0.74 using data in 1.C.E. With an $\alpha=0.05$, 10 clusters per arm will provide 90% power to detect a risk difference of 12% from the intervention.

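### The new-clients-only fallback claims at least 80% power with no control rate; under the plan's own clustering values this holds only below about 9–11%, and power at the 20% trigger rate is about 42% or 67%

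*Combined protocol and SAP*

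**What the plan says.** Section 11 (Aim 2 limitations, new versus all FP clients) sets a fallback: "if Aim 1 screening prevalence is higher than expected (we anticipate a cut-off of around 20% screening prevalence"), Aim 2 will use new clients only, because including existing clients could cause misclassification. It then says "Ten clinics per arm in the RCT with only 60 new clients per clinic would provide at least 80% power"; the effect in question is an absolute difference of 12 percentage points. No control rate, κ or ICC accompanies this figure. The cluster size is sourced as follows: "Preliminary data suggest an average of 60 new FP clients per clinic in a 3-month period (C.1.E").

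The only planning values for Aim 2 are in section 5, for the main analysis: 8% screened in control clinics, 20% after the intervention, 183 clients per clinic, 10 clinics per arm, alpha 0.05 and 90% power. κ is set at 0.5 "to be conservative, which translates to an intra-class correlation coefficient of approximately 0.05". Section 5 also gives a clinic-size variability of 0.74.

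A later limitation in section 11, on identifying women who should be screened, allows the same restriction by a second route with no prevalence threshold: "or only include new FP clients as outlined in the first limitation".

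**The concern.** The fallback applies only when screening is already common, but the power figure attached to it looks as if it was carried over from a calculation in which screening is rare. With a fixed absolute difference, power falls as the control rate rises. The binomial variance grows and, with κ held fixed, so does the between-clinic variance.

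If the switch is made, readers will believe that the trial keeps at least 80% power when it may have much less. A null result could then be read as evidence against SAIA when the trial was unlikely to detect the planned effect. The reason given for the restriction (misclassification) is not in dispute; only the power sentence is.

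**Working it through.** **Inputs.** From section 11: c = 10 clinics per arm, m = 60 new clients per clinic, d = 0.12. From section 5: κ = 0.5, ICC = 0.05, alpha = 0.05 (taken as two-sided; the plan does not say). κ is used as the between-clinic coefficient of variation of the true proportion.

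**Formulas.**
- κ method: V = p0(1−p0)/m + p1(1−p1)/m + κ²(p0² + p1²); power = Φ(√[(c−1)d²/V] − 1.96).
- ICC method (equal clinic sizes): DE = 1 + (m−1)·ICC; V = DE·[p0(1−p0) + p1(1−p1)]/(c·m); power = Φ(d/√V − 1.96).

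**Step 1: the plan's main figure.** At 8% versus 20% with m = 183, the two methods give 88.7% and 91.7%, against the stated 90%. The formulas therefore match the plan's approach.

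**Step 2: the fallback figure at 8% versus 20%, m = 60.**
- κ: V = 0.2336/60 + 0.25 × 0.0464 = 0.01549; √(9 × 0.0144/0.01549) = 2.892; power = Φ(0.932) = 82.4%.
- ICC: DE = 1 + 59 × 0.05 = 3.95; V = 3.95 × 0.2336/600 = 0.001538; 0.12/√V = 3.060; power = Φ(1.100) = 86.4%.

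So the claim of at least 80% reproduces at the main-design rates. That it was computed there is an inference.

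**Step 3: the trigger rate, 20% versus 32%, m = 60.**
- κ: V = 0.3776/60 + 0.25 × 0.1424 = 0.04189; √(0.1296/0.04189) = 1.759; power = Φ(−0.201) = 42.0%.
- ICC: V = 3.95 × 0.3776/600 = 0.002486; 0.12/√V = 2.407; power = Φ(0.447) = 67.3%.

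**Step 4: across control rates** (12-point difference, m = 60).

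| Control rate | κ = 0.5 | ICC 0.05 |
|---|---|---|
| 8% | 82% | 86% |
| 10% | 74% | 82% |
| 15% | 56% | 74% |
| 20% | 42% | 67% |

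Power crosses 80% at a control rate of 8.6% (κ = 0.5) or 11.3% (ICC 0.05).

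**Step 5: more clients.** Sixty per quarter over 12 months is 240 per clinic. At 20% versus 32% this gives 46% (κ) or 76% (ICC), and the 80% crossing points move to 10.5% and 16.4%. With unlimited clients the figures are 48% and 79%, so neither 12 nor 18 months of accrual restores 80% at a 20% control rate.

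**Step 6: what 80% would need at a 20% control rate.** With 60 clients, κ must be at most about 0.27 or ICC at most about 0.032; with 240, κ at most about 0.32 or ICC at most about 0.045. With the plan's clustering values, the difference detectable with 80% power is 23.7 points (κ) or 14.1 points (ICC) with 60 clients, and 22.1 or 12.7 points with 240.

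**Step 7: unequal clinic sizes.** Applying the size variability of 0.74 to the ICC method at 20% versus 32%, m = 60, lowers 67% to about 52% (client-weighted) or 62% (information-weighted, assuming gamma-distributed sizes).

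**κ and ICC are separate assumptions.** ICC = κ²p/(1−p), so κ = 0.5 implies ICC 0.022 at 8%, 0.0625 at 20% and 0.118 at 32%. The two columns are not the ends of one range.

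**Source of the 60.** Section 11 cites C.1.E, which gives no new-client count. C.1.D gives a "mean of 73 new clients per clinic (standard deviation [SD] 81"). Using 73 changes little: 43% and 69% at 20% versus 32%.

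**The case against.** The strongest reply is that the 20% control rate is not the plan's. The trigger is measured in all clients, over 12 months and with other clinic logs added. New clients enter the trial throughout the period and so have shorter follow-up, and Aim 2 expects to use FP registers. If screening occurred at a constant rate and clients entered uniformly over a year, 20% at 12 months would average about 10.4%. Power would then be 80% (κ) or 89% (ICC) with 240 clients, and 73% or 82% with 60. This stands as a possibility: the shortfall is conditional. But the plan states no such rate, and if screening happens mostly at the first visit the rate would be nearer 20%.

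Second, κ = 0.5 was chosen as conservative. At κ = 0.25, which section 5 mentions from the literature, power at 20% versus 32% is 83% with 60 clients and 94% with 240. Restricted or stratified randomization and the longitudinal analysis might also help. All of that is fair, but section 5 adopts 0.5, section 11 names no other value, and no gain from the randomization or the analysis is quantified.

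Third, the scenario is unlikely: preliminary screening was 0.6–1%, and the plan expects very low prevalence. The second route to the restriction has no threshold, so it could apply at low rates where the claim holds. Both points limit the consequence. Neither supports the figure in the scenario for which section 11 offers it.

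**Conclusion.** The concern holds. The figure of at least 80% is correct arithmetic at an 8% control rate, but it is attached to a contingency defined by prevalence of around 20% or more. Under the plan's own clustering values it fails above a control rate of roughly 9–11% with 60 clients per clinic, or 10.5–16.4% with 240, all below the trigger. At 20%, power is about 42% or 67%.

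This rests on a two-sided alpha of 0.05, equal clinic sizes for the ICC figures, and a new-client control rate near 20%, which is an assumption. A lower new-client rate or weaker clustering would narrow or remove the shortfall, but the plan states neither. The main Aim 2 design and its power statement are not affected.

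**What to change.** In section 11, state the control rate and clustering value behind the fallback power, and replace the claim of at least 80%. Possible wording:

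> With 10 clinics per arm and 60 new clients per clinic, power for a 12-point difference is about 42% (κ = 0.5) or 67% (ICC 0.05, equal clinic sizes) if the control rate among new clients is 20%, 56% or 74% if it is 15%, and 74% or 82% if it is 10%. At a 20% control rate, the difference detectable with 80% power is about 24 points (κ = 0.5) or 14 points (ICC 0.05).

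If restricted or stratified randomization is expected to reduce clustering, give the value assumed. Report the new-client screening rate from Aim 1 and recompute the figure with it before any switch is made. Correct the cited source of the new-client count.

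The cost is wording in section 11 and one tabulation of Aim 1 data; new or return status is already among the abstracted variables (section 7). The stated power becomes less favourable. Nothing in the design changes.

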12. STUDY RESULTS DISSEMINATION PLAN

Results of this study will be published so that the research community and public will have access to it. All publications and presentations of material and data related to this study will include acknowledgement of NIH grant support and a disclaimer following NIH guidelines. In accordance with NIH Public Access Policy, all publications will be submitted to PubMed Central.

Data from this study will be available upon request after publication of the main study manuscripts. A standard approach will be followed for data sharing. Researchers requesting access to data will need to first submit a request in writing describing their qualifications, local IRB approval for the planned analyses, statistical analysis plans, and plans to secure the confidentiality and safety of the data. They will be required to agree, in writing, that they will not share the data with others, will use it only for the research purpose(s) delineated, and will return or destroy the data upon completion. All data will be de-identified. Approval from the Kenyatta National Hospital-University of Nairobi Ethics and Research Committee (KNH-UON ERC) will also be required to have access to any data.

We will not develop any unique research resources, inventions, or patents as a result of this work.

F. PERSONNEL

[name], MPH, principal investigator (PI): [name] is an acting instructor in the Department of Medicine at the University of Washington. She has worked previously with her mentor, [name], in leading implementation of his grant in family planning (FP) clinics in Mombasa County. This project is testing an implementation science tool to improve HIV testing in FP clinics. She will provide study oversight and act as the main implementer of the study.

R. [name], MPH, mentor to principal investigator: [name] is Professor of Medicine, Epidemiology and Global Health at the University of Washington. He is also a Visiting Lecturer, Department of Medical Microbiology, University of Nairobi. [name] is the site leader for the Mombasa Cohort, a long-term open cohort study of female sex workers at risk for HIV and STIs. He has studies heterosexual transmission of HIV-1 in Kenya since 1998. [name] will serve as the mentor for [name] for this study. He will provide mentorship and study oversight.

All the proposed research activities involving human subjects will occur in Mombasa County, Kenya. This is in collaboration with Mombasa County Department of Health, and will provide real-time input and sharing of results. Given the location of this study in Mombasa County, we expect that all participants will be of African descent. The FP clinic staff and managers will be both men and women. All FP clients eligible for cervical cancer screening are expected to be women aged 21-65 years.

This study will be conducted in collaboration with the Mombasa County Department of Health (DOH). Dissemination of results will be implemented in collaboration with representatives from the Mombasa County Department of Health.

2. Research Material Obtained from Participants

Family planning registers: Routinely collected data will be abstracted from FP registers about basic demographics, HIV status, cervical cancer screening and referrals of FP clients.

Family planning clinic managers and staff: Family planning clinic managers and staff will be approached to participate in brief semi-structured interviews and in-depth interviews in clinics chosen for the RCT. Managers will be asked to provide verbal assent for semi structure interviews. Clinic staff participating in IDIs will be asked to sign written informed consent. These interviews will be recorded and detailed field notes will be collected by the interviewer.

Data Management: Abstracted FP register data will be uploaded to a REDCap database. Again, there will be no personal identifiable data collected or uploaded. Interview data will be transcribed and translated. These data will be stored on a password protected encrypted computer. Data that have not been decrypted appear as blank files. Interview recordings will be destroyed five years after completion of the research. Informed consent documents will be stored in a locked cabinet and separate from both recordings and transcripts from interviews.

3. Recruitment of Subjects and Consent Procedures

Recruitment of Subjects:

Individual FP clinics will be approached after the sub-county Ministries of Health are aware of the study. A letter of introduction from the Mombasa County Department of Health will accompany study staff. Clinic managers will assent to the preliminary clinic review and then if selected to be randomized into the study.

Clinic managers and clinic staff will be approached by study staff to discuss participating in in-depth interviews. Study staff will identify clinic managers and staff by visiting the clinic and asking for the clinic 'in-charges'. Staff will ask the clinic managers when would be an appropriate time to answer brief questions for Aim 1 and Aim 3 brief structured interviews. Aim

2 in-depth interviews will be scheduled at a time and place convenient to the clinic members. Individual health workers will be recruited confidentially at a convenient time in their work day. They will be reassured that they are free to decline to participate.

Consent procedures:

Family planning clients: As only FP register data will be used, individual FP clients will not be participating in this study. We will use a unique code number to track women over the year in the FP register for outcome data. Client names and contact information will be covered during image capture and for storage. Personal data will be de-identified upon entry into a database as aggregated data. Digital records will include a unique code without personal identifying information.

Family planning clinics: Using previously successful procedures with FP clinics during the FP HIV SAIA trial, FP clinic managers will be approached. Study staff will explain the study and ask that FP clinic manager provide assent to participate in the study.

Family planning clinic managers and staff: Semi-structured interviews and IDIs with health workers will be conducted in confidential settings either within FP clinics, their associated facilities, or at our research facilities, depending on the space available on-site at the different clinics. Individual health workers will be recruited confidentially at a convenient time in their work day. They will be reassured that they are free to decline to participate. Clinic managers participating in semi-structured interviews will be asked to provide verbal assent as these interviews are anticipated to be brief. Health workers who agree to participate in IDIs will be asked to provide written informed consent. The consent forms will be approved in advance by the Kenyatta National Hospital-University of Nairobi Ethics and Research Committee (KNH-UoN ERC) and the University of Washington Human Subjects Research Committee (UW HSRC). Informed consent procedures will be completed prior to initiating the interview. The consent form will include the possibility of negative consequences regarding employment if staff members are identified as providing negative information about the workplace.

This consent process includes the following procedures:

- Ensure that the consent process is taking place in a private area.
- Use the informed consent checklist as a guide throughout the consent process and enter the time at the beginning of the sheet.
- Give the consent form for the client (FP clinic staff member) to read in their language of choice (English or Kiswahili) and allow enough time for the staff member to read the consent form.
- After the potential participant reads the consent/has it read to her, review the key points.
- Ask the potential participant if they have any questions and discuss any questions or concerns.
- Clarify any misunderstanding and determine eligibility.
- Once eligibility is determined the counselor can proceed with the consent process.
- Sign the informed consent checklist and retain if the staff member enrolls
- The potential participant should sign and date first and must write her/his own name. The person obtaining consent signs last.

Potential participants must demonstrate their understanding of key concepts about the informed consent before signing. Specific questions used to assess understanding may include items such as:

1. Please describe what your role will be in this research study?
2. Is participation in these interviews voluntary?

3. If you do not participate, will this reflect negatively in your work evaluations or job status?

The consent form will include the possibility of negative consequences regarding employment if staff members are identified as providing negative information about the workplace. We will also explain how we plan to keep these data confidential.

4. Risk to Human Subjects

No adverse effects would be expected to result directly from the semi-structured interviews or observation of clinic procedures. However, there is potential for negative consequences regarding employment for staff if they are identified as providing negative information about the workplace. This could take the form of harassment, transfer, lack of promotion, dismissal, etc. Staff in smaller facilities might be particularly at risk for inadvertent disclosure if the content of their interviews identified them as being in a particular position. Several steps will be taken to mitigate this risk, as detailed in the section, "Adequacy of Protection against Risks".

For patients accessing care through FP clinics, the risks associated with these services will not be different from the risks associated with these interventions in the absence of the research. Data will be abstracted from routinely collected data in FP registers. While this is personal identifiable data in the FP registers, a unique code will be used to track women over time in the register.

5. Adequacy of Protection Against Risks

Family planning clients: For patients accessing care through FP clinics, the risks associated with these services will not be different from the risks associated with these interventions in the absence of the research. Data will be abstracted from routinely collected data in FP registers. While this is personal identifiable data in the FP registers, a unique code will be used to track women over time in the register. Personal names and contact information will be covered and only the unique code will be used. Images captured will have the unique code but no other personal identifying information. Data entered into the database will be aggregated.

FP clinic managers and staff: Brief semi-structured interviews will ask specific questions and record these answers on data collection forms. We do not anticipate that these questions would be sensitive. As more sensitive information is collected for IDIs, these procedures are slightly different. Health worker names will not be recorded in any location except on their informed consent form. Completed informed consent documents will be stored in a locked cabinet within a locked data room at our research facilities in Mombasa. No other personal identifying information will be collected. To further protect facility staff from negative repercussions if they report workplace problems, several additional steps will be taken as needed:

- Staff will be specifically informed of potential risks during the written informed consent process, and will be assured that they may decline to participate
- We will not inform supervisors of staff members decision to participate or decline participation in the interviews
- Data from multiple staff members may be aggregated into a single report for the purposes of discussion, development of best practices, quality improvement steps, etc.
- Participants will be asked, at the end of each interview, if they have concerns about the use of these data within the framework of the protections noted above. If so, these concerns will be taken into account in making decisions about whether/how to utilize these data.
- On the informed consent document, we will provide telephone numbers for contacting both the research team and the ethics committee if an employee feels that they are

being treated unfairly as a result of participation in the research. If such an event occurs, we will work with our partners in the Mombasa County DOH to take steps to correct the problem and add protections against recurrence.

Health worker IDIs will be recorded, and detailed field notes will be collected by the interviewer. Interview data will be stored on a password-protected encrypted computer. Data that have not been decrypted appear as blank files. Interview recordings will be destroyed at the completion of the research.

6. Potential Benefits

Benefits to all Subjects:

The initial cervical cancer screening care cascade will be presented to Mombasa County. This presentation will inform the County of the current screening activities that may highlight areas for continued important. In addition, comparing the FP registers with DHIS report will provide the County with information about the current state of register documentation. If data quality is not consistent and there is not enough correlation between registers and DHIS reports, it might serve as an impetus for further guidance on appropriate documentation to all FP clinics.

All clinics that could be randomized will have a performance evaluation of cervical cancer screening procedures completed. This evaluation alone is useful quality assurance information for the clinic. Clinics could then act independently to make changes to procedures to increase cervical cancer screening.

Benefits to Subjects in the Intervention Arm of the Trial:

Clinics in the intervention arm will have the benefit of in-depth review of procedures and then SAIA interventions that aims to increase cervical cancer screening. This will benefit individual clinic attendees who may be due for screening **or have never been screened for cervical cancer. Attempts will also be made to make sure that if women are screened by their FP clinics and have an abnormal screen that they are linked with follow-up care.**

The increase in cervical cancer screening and improvement of mechanisms to continue to screen women using SAIA will continue to benefit women and their reproductive health.

7. Importance of knowledge to be gained:

If successful, this research will provide tools that will assist health care workers and managers to understand and improve systems for integrating cervical cancer screening into FP services. The initial cervical cancer care cascade is valuable information for the County to understand the current state of screening and the quality of cervical cancer screening documentation. The SAIA intervention will be conducted in collaboration with local health authorities, and could be scaled up throughout Kenya and in other high burden African countries. Further, the budget impact analysis of SAIA will provide useful information for both the local and national Ministries of Health to use in scaling up cervical cancer screening. The risks to participants are minimal, while the benefits to individual FP clinic clients and the broader population of HIV-positive and HIV-negative women are substantial.

8. Data safety and monitoring plan

The Principle Investigator will take responsibility for data safety and monitoring as part of the oversight of this study. Information collected from FP clients and FP clinic managers will all be de-identified upon storage. Because we will not be enrolling individual participants for the RCT, and individual participant data entered into our dataset will not contain personally identifiable information, we believe this trial does not require a DSMB. This is in conversation with NIH NCI Program Officer. However, if data safety issues arise, these would be reported promptly to both the Kenyatta National Hospital-University of Nairobi Ethics and Research

Committee and the University of Washington Human Subjects Research Committee.

9. Clinical trial registration

This trial has been registered with clinicaltrials.gov

J. BUDGET

Category	Anticipated Amount in USD (Year 1)	Anticipated Amount in USD (Year 2)	Anticipated Amount in USD (Year 3)	Anticipated Amount in USD (Year 4)
Materials and Supplies	\$6679.00	\$6679.00	\$6479.00	\$6479.00
Consultant services	\$1500.00	\$1500.00	\$1500.00	\$1500.00
Communications	\$1000.00	\$1000.00	\$1000.00	\$1000.00
Transportation/travel	\$2000.00	\$2000.00	\$2000.00	\$2000.00
One computer	\$2000.00			
UW-Kenya employees and service fee	\$29,821.00	\$29,821.00	\$29,821.00	\$29,821.00
Total costs:	\$43,000.00	\$41,000.00	\$40,800.00	\$40,800.00

K. APPENDICES

Informed consent documents

Letter from [name]

Curriculum vitae attached for principal investigators and co-investigators
